14.6. Safety Endpoints

Adverse events will be coded using the MedDRA coding dictionary. Incidence of each system organ class and unique preferred term will be tabulated. AE incidence will also be tabulated according to relationship to study medication and severity (graded according to NCI CTCAE v5.0). Serious AEs and AEs resulting in premature discontinuation will be tabulated. AESIs will be tabulated along with all events as well as separately.

Confidential Page 86 of 97

Clinical Study Protocol: AXO-GM2-001

Version 8.0, 09 June 2023

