	Participant (J)	4.70E+13 vg	1.71E+14 vg	2.18E+14 vg
Cohort 1	Participant (I)	4.70E+13 vg	1.71E+14 vg	2.18E+14 vg
(Mid-Dose)	Participant (I)	4.70E+13 vg	1.71E+14 vg	2.18E+14 vg
	Participant (I)	8.15E+13 vg	2.74E+14 vg	3.56E+14 vg
Cohort 2 (High-Dose)	Participant (I)	8.15E+13 vg	2.74E+14 vg	3.56E+14 vg

Note: Dosing based on final titer of 3.26E+13 vg/mL (1:1 mixture of AAVrh8-HEXA:AAVrh8-HEXB)

Stage 2 dosing regimen will be determined based on Stage 1 results.

Duration of treatment: AXO-AAV-GM2 will be administered as a single, two-part procedure

Reference Therapy, Dosage and Mode of Administration: N/A

Criteria for Evaluation:

Stage 1

Stage 1 Primary Endpoint:

• The incidence, severity, seriousness, and relatedness to treatment of treatment emergent adverse events (TEAEs) as graded NCI CTCAE v5.0

Stage 1 Secondary Endpoints:

- Safety and immunologic response endpoints
- Changes in vital signs including weight
- Changes in physical examination findings
- Changes in clinical safety laboratory tests
- Immunosuppression response markers

Stage 1 Exploratory Endpoints:

- Changes from baseline in developmental age-appropriate clinical function assessments
 - Infantile participants: Bayley Scales of Infant and Toddler Development, Third
 Edition (BSID-III), Hammersmith Infant Neurological Examination Section 2
 (HINE-2; motor), Clinical Global Impression (CGI), Vineland-3 Neurological exam

Confidential Page 13 of 97

Version 8.0, 09 June 2023

- Juvenile participants: Neurocognitive function (as measured by the Wechsler, WPSSI, BSID-III depending on the participant's developmental age), Vineland-3, CGI, Neurological exam, fine and gross motor function and classification (as measured by GMFM-88, GMFC-MLD, timed motor function tests, 9-hole peg test, and the Manual Ability Classification System (MACS))
- Biomarker changes from baseline in:
 - Serum HEXA activity level
 - CSF HEXA activity level
 - GM2 ganglioside in CSF
- Change from baseline in brainstem auditory evoked response (BAER) and visual evoked response (VER) from baseline to Week 12 and Week 48
- MRI brain volume and Diffusion Tensor Imaging (DTI) indices of myelination and brain water change from baseline to Week 12 and Week 48
- MRS indices of metabolite accumulation change from baseline to Week 12 and Week 48

Stage 1 Juvenile-Onset Participant Efficacy:

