 Continued assessment of Stage 1 and Stage 2 endpoints for a total of 5 years post-gene transfer

Statistical Methods:

The statistical analysis methods for Stage 1 and Stage 2 will reflect the design elements and objectives of each Stage, with descriptive methods and data listings the primary methods used for the Stage 1 data. The appropriate statistical models and analyses for Stage 2 will be informed by and developed based on the data from Stage 1. Potential comparison of outcomes to external control data may be performed and will be described in the statistical analysis plan.

Sample Size:

- Stage 1: The objectives of Stage 1 are to evaluate safety and tolerability of AXO-AAV-GM2 and identify the optimal dose regimen to be used in Stage 2. The sample size of 12 participants including infantile and juvenile participants is expected to be sufficient to allow assessment of both the safety of the neurosurgical procedure and the stepwise evaluation of escalating BiTh and ICM/IT doses. Furthermore, biomarker, imaging and clinical data collected in Stage 1 are intended to inform the appropriate dose to progress to Stage 2.
- Stage 2: The Primary Efficacy Endpoints for Stage 2 will be the BSID-III Gross Motor domain change from baseline to Week 48 (12 months) and CSF HexA activity change from baseline to Week 48 (12 months). The sample size of up to 10 participants is not based upon

Confidential Page 15 of 97

UMass Chan Medical School AXO-AAV-GM2

Clinical Study Protocol: AXO-GM2-001

Version 8.0, 09 June 2023

hypothesis testing assumptions but rather the desire to assess neurodevelopment of participants at ages when they would be expected to be declining based on natural history data.

General Methods:

Stage 1 outcomes analysis will focus on comparisons of individual participant data using graphical displays (e.g., line-scatterplots of each participant's outcomes over time) to allow for visual inspection of any trends between the participants and within participants over time.

Stage 2 will include a comprehensive assessment of both efficacy and safety outcomes tabulated and presented using both descriptive and inferential statistics (where applicable) where specified.

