UMass Chan Medical School Clinical Study Protocol: AXO-GM2-001 Version 8.0, 09 June 2023

Abbreviation or Specialist Term	Explanation
NCI	National Cancer Institute
NHP	Non-human primate
NHS	Natural history study
NIH	National Institute of Health
PBMCs	Peripheral blood mononuclear cells
PBS	Phosphate buffered saline
PICU	Pediatric Intensive Care Unit
PI	Principal Investigator
PML	Progressive multifocal leukoencephalopathy
PO	Per os
PT	Prothrombin time
PTT	Partial thromboplastin time
RBC	Red blood cell
SADE	Serious adverse device effect
SAE	Serious adverse event
SD	Sandhoff disease
SMA	Spinal muscular dystrophy
SOP	Standard operating procedure
TEAE	Treatment emergent adverse event
Th	thalamus
TSD	Tay-Sachs disease
UNL	Upper normal limit
Vd	Volume of distribution
VER	Visual evoked responses
Vi	Volume of infusion
WBC	White blood cell
YO	Year old

Confidential Page 24 of 97 UMass Chan Medical School AXO-AAV-GM2

Clinical Study Protocol: AXO-GM2-001

Version 8.0, 09 June 2023

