9.4. Study Stopping Criteria

Temporary suspension of enrollment and administration of AXO-AAV-GM2 to study participants will result if any of the following occur in the study:

- 1. Death of any participant in which the cause of death is assessed by the investigator as at least possibly related to the AXO-AAV-GM2 or the neurosurgical administration procedure.
- 2. Intracranial hemorrhage related to the BiTh procedure or an event suggestive of or consistent with craniospinal herniation related to the ICM/IT procedure.
- 3. Two or more CTCAE Grade 3 or higher adverse events in any participant that are assessed by the investigator as possibly, probably or definitely related to AXO-AAV-GM2 or the neurosurgical administration procedure

Confidential Page 70 of 97

Clinical Study Protocol: AXO-GM2-001

Version 8.0, 09 June 2023

4. An SAE in any participant where the event is assessed by the investigator as possibly, probably or definitely related to AXO-AAV-GM2 or the neurosurgical administration procedure

The DSMC will review all available safety data for AXO-AAV-GM2 and the neurosurgical administration/infusion procedures and will make recommendation(s) regarding further study conduct. The DSMC may make a recommendation regarding dose de-escalation/escalation. The clinical study may resume after appropriate steps are taken to address these AEs, including revision of the clinical protocol. Any participants who have already received IMP and are currently in the study at the time study stopping criteria are met will continue to be followed-up, for safety and any signs of efficacy, per protocol.

Confidential Page 71 of 97

Version 8.0, 09 June 2023

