13.9. Adverse and Serious Adverse Events

13.9.1. Definition of Adverse Events

13.9.1.1. Adverse Event (AE)

According to the International Conference of Harmonization (ICH) guideline for Good Clinical Practice, an AE is any untoward medical occurrence in a patient administered pharmaceutical product and which does not necessarily have a causal relationship with this treatment.

An AE can therefore be any of the following:

- Unfavorable and unintended sign (including an abnormal laboratory finding), symptom, or disease temporally associated with the use of a medicinal (investigational) product, whether or not considered related to the medicinal (investigational) product.
- Any new disease or exacerbation of an existing disease (a worsening in the character, frequency, or severity of a known condition)
- Recurrence of an intermittent medical condition (e.g., headache) no present at baseline
- Any deterioration or abnormality in a laboratory value or other clinical test (e.g., ECG, X-ray) that is associated with symptoms or leads to a change in the study treatment or concomitant treatment or discontinuation from the study drug
- Adverse events that are related to a protocol-mandated intervention, including those that occur prior to assignment of study treatment.

All AEs will be captured following the signing of the informed consent form.

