13.10. Relationship to Investigational Product, Study Procedure and Administration System

An Investigator who is qualified in medicine must make the determination of relationship between an AE and the investigational product received, study procedure and/or administration system (e.g., not related, unlikely related, possibly related, probably related, or definitely related). The Investigator should decide whether, in his or her medical judgment, there is a reasonable possibility that the event may have been caused by the investigational product, study procedure and/or administration system.

If there is any valid reason, even if undetermined, for suspecting a possible cause-and-effect relationship between the investigational product and the occurrence of the AE, then the AE should be considered "related."

If the relationship between the AE/SAE and the investigational product is determined to be "possible" or "probable" the event will be considered to be related to the investigational product for the purposes of expedited regulatory reporting.

When assessing a potential relationship between the investigational product, study procedure and/or administration system and an AE, the following parameters should be considered:

- Temporal relationship between the investigational product, surgical procedure and/or protocol-specified procedures and the AE
- The biological plausibility that the investigational product, study procedure and/or administration system caused the event

Confidential Page 80 of 97

AXO-AAV-GM2

UMass Chan Medical School Clinical Study Protocol: AXO-GM2-001

Version 8.0, 09 June 2023

- Any underlying/concurrent illness in the participant
- Concomitant medications the participant may have received
- How commonly the event occurs in the study population independent of treatment

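### Section 14.6 tabulates AE relatedness to study medication only and sets no treatment-emergent limit, unlike the TEAE endpoint and the three-way causality rating in 13.10

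*Combined protocol and SAP*

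**What the plan says.** - **Endpoint.** The Synopsis gives the Stage 1 primary endpoint as "The incidence, severity, seriousness, and relatedness to treatment of treatment emergent adverse events (TEAEs) as graded NCI CTCAE v5.0".
- **Definition of TEAE.** Section 3 only spells out the abbreviation, as "Treatment emergent adverse event". No onset rule appears in the text supplied.
- **Capture.** Section 13.9.1.1 states: "All AEs will be captured following the signing of the informed consent form". The same section counts events tied to protocol-mandated interventions as AEs even when they precede study treatment. Section 13.11 continues collection to the end of long-term follow-up.
- **Causality as rated.** Section 13.10 requires a judgement on the "relationship between an AE and the investigational product received, study procedure and/or administration system".
- **Causality in the stopping rules.** The related-SAE and Grade 3 criteria in Section 9.4 use events "possibly, probably or definitely related to AXO-AAV-GM2 or the neurosurgical administration procedure".
- **Sample size.** The Synopsis says the 12 Stage 1 participants are "expected to be sufficient to allow assessment of both the safety of the neurosurgical procedure" and the stepwise evaluation of doses.
- **Analysis.** Section 14.6 says "Incidence of each system organ class and unique preferred term will be tabulated", and then that "AE incidence will also be tabulated according to relationship to study medication and severity". It also tabulates SAEs, AEs leading to discontinuation, and AESIs, the last both among all events and on their own.

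**The concern.** The treatment is delivered by two neurosurgical procedures on consecutive days, so harm from catheter placement, infusion pressure or lumbar access is a main hazard alongside the vector. The protocol recognises this in the causality rating, the stopping rules and the Stage 1 sample-size rationale. The one relatedness table it describes names only study medication. An event judged unrelated to the vector but definitely related to the procedure or device has no stated place there as a related event.

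The incidence tables have a second gap. The endpoint is treatment-emergent events, but the tables cover adverse events without an onset limit, and collection starts at consent, weeks before dosing. The reported related-AE rate could therefore be too low and the overall AE rate too high, and the tables as described would not show either.

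**Working it through.** The plan states no figure on this point, so the check is a comparison of passages with arithmetic for scale only.

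**1. Relatedness**

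| Place | Causes covered |
|---|---|
| 13.10, rating by the investigator | product, study procedure, administration system |
| 9.4, stopping criteria | product or neurosurgical administration procedure |
| 14.6, planned table | study medication |

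Take one serious event rated unrelated to the vector and definitely related to the neurosurgical procedure. Under the SAE criterion in 9.4 it suspends enrolment and dosing. Under 14.6 it appears in the incidence and SAE tables, but it is not related to study medication on the ordinary reading of that phrase, and no other attribution is specified.

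The AESI list in 13.9.1.3 recovers part of this. It includes neurosurgical complications, and infusion-related reactions defined by timing within a day of infusion. These stay visible whatever their rated cause. Procedure- or device-related events outside that list do not, for example one at a follow-up lumbar puncture or an imaging session under anaesthesia. No attribution is specified for the separate AESI table.

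**2. Event set**

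The Safety Population in 14.3 selects participants who were dosed; it does not select events by onset date. Nothing in 14.6 does so either. Pre-dose events of a child who is later dosed therefore qualify for the incidence table as written.

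The pre-dose window depends on when counting starts (Tables 14 and 15):

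- Consent at Visit A, Week -8 ± 28 days: 56 - 28 = 28 days to 56 + 28 = 84 days. As a share of the time from consent to the 4-week safety review, this is 28/(28 + 28) = 50% to 84/(84 + 28) = 75%.
- First scheduled AE review at Visit B, Day -16 ± 5 days: about 11 to 21 days, or 11/(11 + 28) = 28% to 21/(21 + 28) = 43%.

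The consent form is marked at both visits, so either start is possible. The longer window includes the Visit A MRI (under general anaesthesia, per 13.6) and CSF collection. Both windows include the start of immunosuppression on Day -7 (8.2).

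**3. Size per participant**

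- Stage 1, 12 planned: 1/12 = 8.3 percentage points.
- Stage 2, up to 10 planned: 1/10 = 10 points at full enrolment.

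A child whose only related event is procedure- or device-related lowers the related incidence by this step. A child whose only event is pre-dose raises the AE incidence by the same step. The documents give no basis for the number of such children.

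**The case against.** **14.6 may not be the Stage 1 analysis.** A reader might infer that the Stage 1 primary endpoint has been given a wrong analysis. Section 14.2 does not support that. It says the methods that follow are mainly for Stage 2 and may apply to Stage 1 in some instances, it makes Stage 1 tabulations optional, and Section 14 makes descriptive methods and listings the main Stage 1 tools. With 12 children, a listing would show each event's date and cause. This stands, and it limits the Stage 1 claim. It does not remove the point: 14.2 names AE incidence as its example of a Stage 1 tabulation, 14.6 is the only AE analysis text supplied, and the same wording governs Stage 2.

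**Safety decisions do not depend on this table.** A reader might infer that the DSMC would see understated risk. Section 17.1 gives the DSMC treatment-emergent safety reports, notice of all SAEs, and review of signals from both product and procedure. Section 9.4 is triggered by individual events, not by a tabulated rate. This objection stands in full.

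**The consequences come from silence.** 14.6 does not say that pre-dose events are included, or that procedure-related events are classed as unrelated, and study medication is undefined. This also stands. The claim is what a literal reading produces, not what the sponsor has declared. The DSMC text suggests that treatment-emergent events are the intended set, which is a reason to say so in 14.6.

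**Conclusion.** The point holds as a mismatch between what the protocol defines and rates and what 14.6 says will be tabulated. Followed literally, the relatedness table omits attribution to procedure and device, and the incidence table has no onset limit. It affects the reported safety result of Stage 2, and of Stage 1 wherever 14.6 is applied under 14.2. It does not affect DSMC review, the stopping decisions, or the visibility of neurosurgical complications and infusion-related reactions as AESIs.

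The size is known only per child: 8.3 points in Stage 1 and 10 points in a full Stage 2. A total bias cannot be stated, because the number of children affected is unknown. The conclusion assumes that study medication means the vector product and that no further AE analysis rules exist outside the text supplied.

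The relatedness part is the weightier of the two, because it concerns a principal hazard of the delivery method. The event-set part also needs a definition that the protocol lacks: TEAE has no onset reference, and the text does not say whether the Day -7 immunosuppression counts as treatment for this purpose.

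**What to change.** Amend 14.6 and state that it applies to both stages.

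1. **Relatedness.** Tabulate it separately for investigational product, study procedure and administration system, and for any of these. Add a subtotal for product or neurosurgical administration procedure, using the causality wording of 9.4. The subtotal is needed because the any-cause column is broader than 9.4: study procedure can include follow-up imaging and lumbar punctures. Neither count reproduces the stopping rule itself, which also depends on grade and seriousness.
2. **Event set.** Define TEAE with an explicit onset reference that says whether the Day -7 immunosuppression counts as treatment. Tabulate TEAEs on that basis and show AEs from consent to that reference in a separate table.

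The cost is protocol wording and an extra table layout. Sections 13.10 and 13.11 already call for the causality judgement and for onset date and time, so no new assessment is needed. The case report form is not in the document; the sponsor should confirm that it stores the causes separately and distinguishes the neurosurgical procedure from other study procedures. The headline related-AE rate may be higher than under the present wording.

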15. ACCESS TO SOURCE DATA/DOCUMENTS FOR MONITORING

In accordance with ICH GCP (ICH E6(R2)) guidelines, CRAs must have direct access to the Investigator's source documentation in order to verify the data recorded in the eCRF. The CRAs are responsible for routine review of the CRFs according to details contained in the Clinical Monitoring Plan (CMP) throughout the study, to verify adherence to the protocol, and the completeness, consistency, and accuracy of the data being entered on them. The CRAs should have access to any participant records needed to verify the entries in the eCRF. The Investigator agrees to cooperate with the CRAs to ensure that any problems detected in the course of these monitoring activities are resolved.

15.1. Audits and Inspections

During the conduct of the study, the sponsor, its representative, and regulatory authorities may conduct audits of any data and any facility participating in the study. The investigator and institutions involved in the study will permit such study-related audits and provide direct access to all study records and facilities. And the investigator agrees to participate in audits conducted at a convenient time in a reasonable manner.

In the event of an inspection by any regulatory authority, the investigator should promptly notify the sponsor.

15.2. Institutional Review Board (IRB)

The Principal Investigator must obtain IRB approval for the investigation from committees within the institution. Initial IRB approval, and all materials approved by the IRB for this study including the participant consent form and recruitment materials must be maintained by the Investigator and made available for inspection.

Confidential Page 87 of 97

Clinical Study Protocol: AXO-GM2-001

Version 8.0, 09 June 2023

16. QUALITY CONTROL AND QUALITY ASSURANCE

16.1. Deviations from Protocol

Protocol deviations, except those intended to reduce immediate risk to study participants, will only be implemented by Sponsor-initiated amendments. IRB/EC approval must be obtained before changes can be implemented.

Confidential Page 88 of 97

UMass Chan Medical School Clinical Study Protocol: AXO-GM2-001 Version 8.0, 09 June 2023

17. STUDY COMMITTEES

17.1. Independent Data and Safety Monitoring Committee (DSMC)

The DSMC is an independent multidisciplinary group (independent of both the sponsor and CRO) who collectively has experience in the management of participating participants as well as in the conduct and monitoring of clinical trials.

The DSMC will meet at regular intervals allowing for the timely review of 4-week safety data for Stage 1 participants (see Section 8.1.1). The DSMC and Sponsor will determine whether enrollment of participants may proceed according to the dose-escalation plan (Table 10). Based on satisfactory review of 4-week safety data for each participant, accrued safety data of all participants, and review for potential safety signals related to AXO-AAV-GM2 as well as that of the neurosurgical administration/infusion procedures, the DSMC may recommend to continue the study as designed, to continue the study with modifications (e.g. dose descalation/escalation in the event of toxicity), or to terminate the study early based on the safety.

After the last Stage 1 participant has been dosed and observed for 4 weeks, the DSMC will review the cumulative safety data in conjunction with the Sponsor and determine the optimal AXO-AAV-GM2 dose regimen to be administered in Stage 2. The DSMC will continue to meet at regular intervals throughout the duration of the study.

The DSMC will review enrollment progress, baseline characteristics of the study population, all treatment-emergent safety reports, clinical laboratory and imaging data. The members of the DSMC will be notified of all SAEs.

Additional details regarding the specifics of the DSMC operations may be found in the DSMC Charter.

Confidential Page 89 of 97

Version 8.0, 09 June 2023

